6.5.1 Immunogenicity Assessments

The following immunogenicity assessments are planned:

- Serum antibody level as measured by HAI assay for primary, secondary, and exploratory analyses
- NA-specific antibody levels as measured by NAI assay for primary, secondary, and exploratory analyses
- Serum neutralizing antibody level as measured by microneutralization (MN) assay or similar method for secondary or exploratory analysis

- Cellular immunogenicity for exploratory subset analysis. No summary table or listing will be provided.

6.5.2 Primary Analysis of Immunogenicity

GMTs and GMFRs:

For each vaccination group, the following evaluations will be performed at Day 1 (if applicable) and Day 29.

- GMT of vaccine-matched strain-specific anti-HA antibodies with corresponding 95% CI will be provided at Day 1 and Day 29, GMT of vaccine-matched strain-specific anti-NA antibodies with corresponding 95% CI will be provided at Day 1 and Day 29, GMFR of vaccine-matched strain-specific anti-HA antibodies with corresponding 95% CI will be provided at Day 29 over pre-injection baseline at Day 1.
- GMFR of vaccine-matched strain-specific anti-NA antibodies with corresponding 95% CI will be provided at Day 29 over pre-injection baseline at Day 1.
- In addition, the following descriptive statistics will also be provided at Day 29: the number of participants (n), median, minimum, and maximum.

Seroconversion:

For each vaccination group, the following evaluations will be performed at Day 29.

- For HA, the number and percentage of participants with seroconversion at Day 29 will be provided with 2-sided 95% CI using the Clopper-Pearson method.

For HA, seroconversion is defined as:

1. If LLOQ is 1:10, a Day 29 titer \geq 1:40 if baseline is < 1:10 or a 4-fold or greater rise if baseline is \geq 1:10 in anti- HA antibodies measured by HAI assay.
2. If LLOQ is greater than 1:10 (e.g. 1:14), a Day 29 titer \geq 4 times of LLOQ if baseline is < LLOQ or a 4-fold or greater rise if baseline is \geq LLOQ in anti- HA antibodies measured by HAI assay.

2-/3-/4-fold Rise:

For NA, an endpoint of interest is the percentage of participants with a change in the

Day 29 titer of at least 2-/3-/4-fold rise from baseline.

Definition: 2-/3-/4-fold rise is defined as \geq 2-/3-/4-fold of the LLOQ if the Day 1 titer is < LLOQ; or \geq 2-/3-/4-fold of the Day 1 titer if the Day 1 titer \geq LLOQ.

For each vaccination group, the following evaluations will be performed at Day 29.

- The number and percentage of participants with a \geq 2-fold rise at Day 29 in anti-NA antibody titers from baseline will be provided with 2-sided 95% CI using the Clopper-Pearson method.
- The number and percentage of participants with a \geq 3-fold rise at Day 29 in anti-NA antibody titers from baseline will be provided with 2-sided 95% CI using the Clopper-Pearson method.
- The number and percentage of participants with a \geq 4-fold rise at Day 29 in anti-NA antibody titers from baseline will be provided with 2-sided 95% CI using the Clopper-Pearson method.

6.5.3 Secondary Analysis of Immunogenicity

For each vaccination group, the following evaluations will be performed at all evaluable humoral immunogenicity time points.

GMTs and GMFRs:

- GMT of vaccine-matched strain-specific anti-HA antibodies with corresponding 95% CI will be provided at each time point,. Geometric mean (GM) level and corresponding 95% CI will be plotted at each time point.
- GMT of vaccine-matched strain-specific anti-NA antibodies with corresponding 95% CI will be provided at each time point.GM level and corresponding 95% CI will be plotted at each time point.
- GMFR of vaccine-matched strain-specific anti-HA antibodies with corresponding 95% CI will be provided at each post-baseline time point over pre-injection baseline at Day 1. GMFR and corresponding 95% CI will be plotted at each time point.
- GMFR of vaccine-matched strain-specific anti-NA antibodies with corresponding 95% CI will be provided at each post-baseline time point over pre-injection

baseline at Day 1. GMFR and corresponding 95% CI will be plotted at each time point.

- In addition, the following descriptive statistics will also be provided at each time point: the number of participants (n), median, minimum, and maximum.
- Reverse cumulative distribution function curve at each time point will be provided.
- Listing of anti-HA antibodies for vaccine-matched seasonal influenza A and B strains will be provided based on the PP Set.
- Listing of anti-HA antibodies for vaccine-matched seasonal influenza A and B strains for participants with influenza infection will be provided based on the PP Set.
- Listing of anti-NA antibodies for vaccine-matched seasonal influenza A and B strains will be provided based on the PP Set.
- Listing of anti-NA antibodies for vaccine-matched seasonal influenza A and B strains for participants with influenza infection will be provided based on the PP Set.

Seroconversion:

For each vaccination group, the following evaluations will be performed at each post-baseline time point.

- For HA, the number and percentage of participants with seroconversion at each post-baseline time point will be provided with 2-sided 95% CI using the Clopper-Pearson method.

2-/3-/4-fold Rise:

For NA: For each vaccination group, the following evaluations will be performed at each post-baseline time point.

- The number and percentage of participants with a \geq 2-fold rise at each post-baseline time point in anti-NA antibody titers from baseline will be provided with 2-sided 95% CI using the Clopper-Pearson method.

- The number and percentage of participants with a ≥ 3 -fold rise at each post-baseline time point in anti-NA antibody titers from baseline will be provided with 2-sided 95% CI using the Clopper-Pearson method.
- The number and percentage of participants with a ≥ 4 -fold rise at each post-baseline time point in anti-NA antibody titers from baseline will be provided with 2-sided 95% CI using the Clopper-Pearson method.

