3.3 Exploratory Endpoints

The exploratory endpoints are as follows:

- GMT and GMFR of anti-HA or anti-NA antibodies as measured by HAI, NAI, and/or MN assays against vaccine-mismatched strains compared with Day 1 (baseline)
- Frequency, magnitude, and phenotype of virus-specific T-cell and B-cell responses measured by flow cytometry or other methods, and to perform targeted repertoire analysis of T-cells and B-cells after vaccination
- Frequency, specificities, or other endpoints to be determined, for the further characterization of antibody responses
- Frequency of clinical influenza and assessment of immune responses in participants with clinical influenza
- Transfer of human sera into mice with subsequent influenza virus challenge to observe protection from morbidity and mortality conferred by NA-specific antibodies

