5.3 Per-Protocol (PP) Set

The PP Set consists of all participants in the FAS who comply with the injection schedule, comply with the timings of immunogenicity blood sampling to have a baseline and at least 1 post-injection assessment, do not have influenza infection at baseline through Day 29 (as documented by PCR testing), and have no major protocol deviations that impact the immune response. The PP Set will be used as the primary analysis set for analyses of immunogenicity unless otherwise specified. Participants will be analyzed according to the vaccination group to which they were randomized.

Participants compliant with the timing of immunogenicity blood sampling are required to have a baseline assessment, at least one post-injection assessment, and a Day 29 assessment that is within 21 days to 42 days after injection (-7 / +14 days of Day 29).

Participants with a dosing error will be considered as having a protocol deviation. However, the determination of whether to include/exclude participants from the PP Set due to a dosing error will be based on the dosage difference (in μ g) between the actual dose received and the randomized dose. The PP Set exclusion criteria for participants with dosing error are described in [Table 2](#). For the mRNA-1020 and the mRNA-1030 arms, acceptable dosing deviation from the randomized dose is up to **CCI** [REDACTED]. For the mRNA-1010 active comparator, participants who are randomized to the active comparator arm but received less than **CCI** [REDACTED] of the active comparator or any amount of mRNA-1020, mRNA-1030, or Flublok active comparator will be excluded from the PP Set. For the Flublok active comparator, participants who are randomized to the active comparator arm but received less than **CCI** [REDACTED] of the active comparator or any amount of mRNA-1020, mRNA-1030, or mRNA-1010 active comparator will be excluded from the PP Set.

Table 2 PP Set Exclusion Criteria for Dosing Errors

	Randomized Dose							
	mRNA-1020	mRNA-1030			mRNA-1010 (active comparator) ¹		Flublok (active comparator) ²	
Actual Dose Received	CCI							
mRNA-1020								
	CCI	Y	Y	Y	Y	Y	Y	Y
	CCI	Y	Y	Y	Y	Y	Y	Y
	CCI	Y	Y	Y	Y	Y	Y	Y
	CCI	Y	Y	Y	Y	Y	Y	Y
	CCI	Y	Y	Y	Y	Y	Y	Y
	CCI	Y	Y	Y	Y	Y	Y	Y
	CCI	Y	Y	Y	Y	Y	Y	Y
	CCI	Y	Y	Y	Y	Y	Y	Y
	CCI	Y	Y	Y	Y	Y	Y	Y
	CCI	Y	Y	Y	Y	Y	Y	Y
	CCI	Y	Y	Y	Y	Y	Y	Y
	CCI	Y	Y	Y	Y	Y	Y	Y
	CCI	Y	Y	Y	Y	Y	Y	Y
	CCI	Y	Y	Y	Y	Y	Y	Y
	CCI	Y	Y	Y	Y	Y	Y	Y
	CCI	Y	Y	Y	Y	Y	Y	Y
	CCI	Y	Y	Y	Y	Y	Y	Y
	CCI	Y	Y	Y	Y	Y	Y	Y
	CCI	Y	Y	Y	Y	Y	Y	Y

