6.5 Immunogenicity Analysis

The analyses of immunogenicity will be based on the PP Set and will be performed by vaccination group and by age group.

If the number of participants in the FAS and PP Set differs (defined as the difference divided by the total number of participants in the PP Set) by more than 10% for each age

group, supportive analyses of immunogenicity may be conducted using the FAS. The supportive analysis is required if the condition is met.

The GMT and geometric mean (GM) level will be calculated using the following formula:

$$2^{\left\{ \frac{\sum_{i=1}^n \log_2(t_i)}{n} \right\}}$$

where t_1, t_2, \dots, t_n are n observed immunogenicity titers or levels.

The GMFR measures the changes in immunogenicity titers or levels within participants. The GMFR will be calculated using the following formula:

$$2^{\left\{ \frac{\sum_{i=1}^n \log_2(v_{ij}/v_{ik})}{n} \right\}} = 2^{\left\{ \frac{\sum_{i=1}^n \log_2(v_{ij}) - \log_2(v_{ik})}{n} \right\}}$$

where, for n participants, v_{ij} and v_{ik} are observed immunogenicity titers or levels for participant i at time points j and $k, j \neq k$.

The 95% CIs for GMT and GMFR will be calculated based on the t distribution of the log-transformed values then back transformed to the original scale for presentation, unless otherwise specified. Reverse cumulative distribution plot will be generated.

The model-based GM titer will be estimated based on an analysis of covariance (ANCOVA) model. In the ANCOVA model, the log-transformed antibody titer at a post baseline timepoint (Day 29) are treated as a dependent variable, with the treatment group as an explanatory variable and the log-transformed baseline antibody titer as a covariate, adjusting for the stratification factor(s) as appropriate, that is, age groups (18 to 49 years old, and 50 to 75 years old of age).

The GMT will be estimated by the geometric least square mean (GLSM) from the ANCOVA model for each treatment group and corresponding 95% CI will be provided.

For each pair of between-group comparison specified in [Table 3](#), the GMR (ratio of GMTs) between the two treatment groups in each pair will be estimated from the ANCOVA model, with 95% CI provided accordingly.

For each pair of between-group comparison specified in [Table 3](#), the difference of seroconversion rate (SCR) between the two treatment groups in each pair at Day 29 will be provided, with 95% CI estimated using Miettinen-Nurminen method.

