6.5.4 Exploratory Analysis of Immunogenicity

The below exploratory analyses of immunogenicity may be performed:

- GMT of vaccine-mismatched strain-specific anti-HA antibodies with corresponding 95% CI will be provided at each time point using methods described in [Section 6.5](#).
- GMT of vaccine-mismatched strain-specific anti-NA antibodies with corresponding 95% CI will be provided at each time point using methods described in [Section 6.5](#).
- GMFR of vaccine-mismatched strain-specific anti-HA antibodies with corresponding 95% CI will be provided at each post-baseline time point over pre-injection baseline at Day 1 using methods described in [Section 6.5](#).
- GMFR of vaccine-mismatched strain-specific anti-NA antibodies with corresponding 95% CI will be provided at each post-baseline time point over pre-injection baseline at Day 1 using methods described in [Section 6.5](#).
- Summary of RT-PCR results at Baseline.
- Summary of detected influenza results by RT-PCR at post-baseline by time period.
- Listing of anti-HA antibodies for vaccine-mismatched influenza A and B strains will be provided based on the PP Set.
- Listing of anti-HA antibodies for vaccine-mismatched influenza A and B strains for participants with influenza infection will be provided based on the PP Set. Listing of anti-NA antibodies for vaccine-mismatched influenza A and B strains will be provided based on the PP Set.
- Listing of anti-NA antibodies for vaccine-mismatched influenza A and B strains for participants with influenza infection will be provided based on the PP Set.

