6.6 Analysis of Influenza Infection

Influenza infection during the study is an exploratory endpoint, and the analyses of influenza infection confirmed by RT-PCR test may be performed using the FAS.

Due to the ongoing COVID-19 pandemic, participants may get infected with SARS-CoV-2 or experience symptoms consistent with influenza-like illness (ILI) during the study.

NP swab samples will be collected from all participants before the injection on Day 1 for assessment of asymptomatic infection with respiratory pathogens, including influenza virus and SARS-CoV-2, as influenza or COVID-19 symptoms may confound reactogenicity assessment. Furthermore, if a participant experiences any signs or symptoms suggesting ILI and/or COVID-19, an additional NP swab sample will be collected to confirm the diagnosis via RT-PCR.

A CDC-defined ILI is defined as body temperature $\geq 37.8^{\circ}\text{C}$ (100°F) accompanied by cough and/or sore throat. An RT-PCR confirmed ILI is defined as a positive influenza result by RT-PCR done at any setting during the study period.

Summaries below will be provided, unless otherwise specified.

- RT-PCR test results at baseline will be summarized by test and vaccination group. Participants with positive influenza results at baseline will be presented in a listing.
- The number and percentage of participants with at least one positive influenza result at post-baseline will be provided by vaccination group. Participants with at least one positive influenza result at post-baseline will be presented in a listing.

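### The four titer listings for influenza-infected participants use the PP Set, which leaves out every PCR-documented infection through Day 29; they should use the FAS.

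*SAP*

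**What the plan says.** - **The listings.** SAP 6.5.3 specifies two titer listings (anti-HA and anti-NA, vaccine-matched strains) that "for participants with influenza infection will be provided based on the PP Set". SAP 6.5.4 does the same for mismatched strains, for example: "Listing of anti-NA antibodies for vaccine-mismatched influenza A and B strains for participants with influenza infection will be provided based on the PP Set".
- **The population.** Under SAP 5.3, PP Set members must be in the FAS and "do not have influenza infection at baseline through Day 29 (as documented by PCR testing"). Protocol Table 8 has the same criterion.
- **Infection analyses.** SAP 6.6 says that "the analyses of influenza infection confirmed by RT-PCR test may be performed using the FAS". Its case definition has no early cut-off: "An RT-PCR confirmed ILI is defined as a positive influenza result by RT-PCR done at any setting during the study period". It plans listings of participants positive at baseline and after baseline, but mentions no titers for them.
- **The endpoint.** SAP 3.3 includes "Frequency of clinical influenza and assessment of immune responses in participants with clinical influenza", with no restriction to infections after Day 29.
- **The back-up.** SAP 6.5 says that "supportive analyses of immunogenicity may be conducted using the FAS", and makes this mandatory only if the FAS and PP Set differ by more than 10% for each age group.

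**The concern.** The listings are meant to show antibody titers in people who had influenza, but they draw on a population defined partly by not having had it during the first 29 days. The cases left out are also those with the most scheduled sampling around infection. Humoral blood is scheduled at Days 1, 8, 29 and 181, so an infection in the first month can be followed by a Day 8 or Day 29 sample. A later one normally has only Day 181. The FAS case listing in SAP 6.6 and the titer listings would then describe different groups of infected participants, and nothing in the SAP tells the reader so.

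At stake is how complete the prespecified output is for one exploratory endpoint.

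**Working it through.** The plan gives no figure to reproduce here. The check is set logic plus a little arithmetic.

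**1. Who can appear in the four listings?** (SAP 5.3 set against 6.5.3 and 6.5.4)

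| PCR-documented influenza | In PP Set? | In the infected-participant titer listings? | In the FAS, as used in SAP 6.6? |
|---|---|---|---|
| At baseline, and vaccinated | No | No | Yes |
| After baseline, through Day 29 | No | No | Yes |
| First positive Day 30 to Day 181 | Yes, if the other PP criteria are met | Yes, if in the PP Set | Yes |

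The other PP criteria (a Day 29 sample 21 to 42 days after injection, no disqualifying dosing error, no major deviation affecting the immune response) can also remove some later cases.

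**2. How much follow-up is excluded?** Days 1 to 29 are 29 days, and Days 30 to 181 are 181 − 29 = 152 days.
- Excluded: 29/181 = 0.160, or 16% of study days.
- Retained: 152/181 = 0.840, or 84%.

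These are shares of calendar time. They equal shares of cases only under a constant infection hazard, and even then baseline positives come on top.

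**3. Which titers follow infection?** The scheduled time points are Days 1, 8, 29 and 181 (protocol Table 1; SAP Appendix B, Table 4). For a first positive after Day 29, the Day 8 sample precedes infection and the Day 29 sample normally does too, leaving Day 181. The word normally is needed because SAP 5.3 accepts a Day 29 sample up to 42 days after injection, so a late draw could follow an infection shortly after Day 29. Protocol Table 1 marks no humoral immunogenicity sample at unscheduled visits.

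**4. What would the interim analysis show?** SAP 6.7 uses data through the Day 29 visit. Infections up to then are almost all inside the excluded window, so the listings would be essentially empty if run at that point. The SAP does not say that they will be.

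**5. Does another output show the early cases' titers?**
- The general titer listings in 6.5.3 and 6.5.4 also use the PP Set.
- SAP 6.6 uses the FAS but specifies no titers.
- The FAS supportive analysis is conditional. Taking the planned 280 participants per age group as the FAS and dividing by the PP Set, as SAP 6.5 defines the difference: 25 exclusions give 25/255 = 9.8% (not triggered), and 26 give 26/254 = 10.2% (triggered). So about 26 exclusions are needed in each age group. With dosing planned for spring, when the protocol expects low or declining influenza rates, infections alone are unlikely to reach that.

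No output is therefore guaranteed to show these titers.

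**The case against.** **The PP Set may be deliberate.** Two of the four listings sit in the secondary analysis, which concerns vaccine immunogenicity over time. A PP listing of infected participants would be useful there: it would identify people infected after Day 29 whose Day 181 titer may reflect infection rather than vaccine. On that reading the text is not contradictory, only silent about its restriction. This is plausible, but the SAP does not say it, and the mismatched-strain listings in 6.5.4 fit the exploratory endpoint better.

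**Different counts are not in themselves an error.** An FAS count and a PP listing will naturally differ, and both populations are disclosed. That stands. The point is that the infected-participant listings are incomplete for the endpoint.

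**Little can be learned from early cases.** A Day 29 titer after infection in the first month mixes vaccine and infection responses, which is a sound reason to keep such participants out of the PP summaries. It is not a reason to omit them from a listing of infected participants, where the date and PP status can be shown. Baseline positives are a weaker case, because the Day 1 swab looks for asymptomatic infection and the endpoint concerns clinical influenza.

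**Nothing is destroyed.** Early cases can be identified from the SAP 6.6 listings and the PP-exclusion summary, their titers remain in the database, and a post hoc FAS listing could be run. This also stands and limits the severity.

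**Conclusion.** The mismatch is real and minor. As written, the four listings omit every participant with PCR-documented influenza from baseline through Day 29, a window covering 16% of study days, and no other prespecified output is certain to show those participants' titers.

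Three stronger readings are tempting, and the documents do not support them:
- **That the listings will always be empty.** Infections first detected from Day 30 to Day 181 can remain in the PP Set and be listed.
- **That a large share of cases, perhaps half, is dropped.** A declining hazard after spring dosing would raise the share above 16%. A hazard halving every 28 days, for example, would give 0.5/(1 − 0.5^(180/28)) = 0.51. But that half-life is arbitrary: the documents give neither a rate of decline nor an attack rate. The number of cases cannot be determined and may be small.
- **That immunogenicity results are biased.** The affected items are listings of individual data. No primary or secondary estimate or confidence interval changes, and the 6.5.4 analyses are themselves optional.

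The conclusion rests only on the SAP's stated populations and the sampling schedule.

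**What to change.** In SAP 6.5.3 and 6.5.4, change the population of the four infected-participant titer listings from the PP Set to the FAS, in line with SAP 6.6. Add two columns: PP Set status, and the date of the positive PCR. A reader who wants the PP view can filter on the flag, so nothing is lost. Leave the PP Set definition and all PP-based summaries as they are.

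If the sponsor meant to show only PP participants infected after Day 29, one sentence saying so would remove the ambiguity, although early cases' titers would still lack a planned listing.

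The cost is a population change and two columns in four listing shells. It needs no new data and does not affect study conduct.

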6.5.4 Exploratory Analysis of Immunogenicity

The below exploratory analyses of immunogenicity may be performed:

- GMT of vaccine-mismatched strain-specific anti-HA antibodies with corresponding 95% CI will be provided at each time point using methods described in [Section 6.5](#).
- GMT of vaccine-mismatched strain-specific anti-NA antibodies with corresponding 95% CI will be provided at each time point using methods described in [Section 6.5](#).
- GMFR of vaccine-mismatched strain-specific anti-HA antibodies with corresponding 95% CI will be provided at each post-baseline time point over pre-injection baseline at Day 1 using methods described in [Section 6.5](#).
- GMFR of vaccine-mismatched strain-specific anti-NA antibodies with corresponding 95% CI will be provided at each post-baseline time point over pre-injection baseline at Day 1 using methods described in [Section 6.5](#).
- Summary of RT-PCR results at Baseline.
- Summary of detected influenza results by RT-PCR at post-baseline by time period.
- Listing of anti-HA antibodies for vaccine-mismatched influenza A and B strains will be provided based on the PP Set.
- Listing of anti-HA antibodies for vaccine-mismatched influenza A and B strains for participants with influenza infection will be provided based on the PP Set. Listing of anti-NA antibodies for vaccine-mismatched influenza A and B strains will be provided based on the PP Set.
- Listing of anti-NA antibodies for vaccine-mismatched influenza A and B strains for participants with influenza infection will be provided based on the PP Set.

